3.6 Post Study Drug Follow up

In this study, PASI-75 is a key endpoint of the study. Post study follow-up is of critical importance and is essential to preserving subject safety and the integrity of the study. Subjects who discontinue study drug must continue to be followed for collection of outcome and/or survival follow-up data as required and in line with [Section 5](#) until death or the conclusion of the study.

3.6.1 Withdrawal of Consent

Subjects who request to discontinue study drug will remain in the study and must continue to be followed for protocol specified follow-up procedures. The only exception to this is when a subject specifically withdraws consent for any further contact with him/her or persons previously authorized by the subject to provide this information. Subjects should notify the investigator of the decision to withdraw consent from future follow-up **in writing**, if possible. The withdrawal of consent should be explained in detail in the medical records by the investigator, as to whether the withdrawal is from further treatment with study drug only or also from study procedures and/or post treatment study follow-up, and entered on the appropriate CRF page. In the event that vital status (whether the subject is alive or dead) is being measured, publicly available information should be used to determine vital status only as appropriately directed in accordance with local law.

3.6.2 Lost to Follow-Up

All reasonable efforts must be made to locate subjects to determine and report their ongoing status. This includes follow-up with persons authorized by the subject as noted above. Lost to follow-up is defined by the inability to reach the subject after a minimum of three documented phone calls, faxes, texts, or emails as well as lack of response by subject to one registered mail letter. All attempts should be documented in the subject's medical records. If it is determined that the subject has died, the site will use permissible local methods to obtain the date and cause of death.

If investigator's use of third-party representative to assist in the follow-up portion of the study has been included in the subject's informed consent, then the investigator may use a sponsor-retained third-party representative to assist site staff with obtaining subject's contact information or other public vital status data necessary to complete the follow-up portion of the study. The site staff and representative will consult publicly available sources, such as public health registries and databases, in order to obtain updated contact information. If after all attempts, the subject remains lost to follow-up, then the last known alive date as determined by the investigator should be reported and documented in the subject's medical records.

4 STUDY DRUG

Study drug includes both investigational [medicinal] product (IP/IMP) and non-investigational [medicinal] product (Non-IP/Non-IMP) and can consist of the following:

- All products, active or placebo, being tested or used as a comparator in a clinical trial.
- Study required premedication, and
- Other drugs administered as part of the study that are critical to claims of efficacy (eg, background therapy, rescue medications)
- Diagnostic agents: (such as glucose for glucose challenge) given as part of the protocol requirements must also be included in the dosing data collection

Table 4-1: Study Drugs for IM011011

Product Description Class and Dosage Form	Potency	IP/Non-IMP	Blinded or Open Label	Packaging/Appearance	Storage Conditions (per label)
BMS-986165 capsule	3 mg (as the free base)	IP	Blinded	Blister Card containing 48 active (3mg) and/or placebo capsules to equal required subject daily dosing/ Size #1 hard gelatin capsule	Store 2 to 8°C ; Protected from light
Placebo Matching BMS-986165 capsule	N/A	IP	Blinded	Blister Card containing 48 active (3mg) and/or placebo capsules to equal required subject daily dosing/ Size #1 hard gelatin capsule	Store 2 to 8°C ; Protected from light

4.1 Investigational Product

An investigational product, also known as investigational medicinal product in some regions, is defined as a pharmaceutical form of an active substance or placebo being tested or used as a reference in a clinical study, including products already with a marketing authorization but used or assembled (formulated or packaged) differently than the authorized form, or used for an unauthorized indication, or when used to gain further information about the authorized form.

The investigational product should be stored in a secure area according to local regulations. It is the responsibility of the investigator to ensure that investigational product is only dispensed to study subjects. The investigational product must be dispensed only from official study sites by authorized personnel according to local regulations.

4.2 Non-investigational Product

Other medications used as support or escape medication for preventative, diagnostic, or therapeutic reasons, as components of the standard of care for a given diagnosis, may be considered as non-investigational products. Not applicable for this study.

4.3 Storage of Study Drug

The product storage manager should ensure that the study drug is stored in accordance with the environmental conditions (temperature, light, and humidity) as determined by BMS (see [Table 4-1](#)). If concerns regarding the quality or appearance of the study drug arise, the study drug should not be dispensed and contact BMS immediately.

Study drug not supplied by BMS will be stored in accordance with the package insert.

Please refer to [Section 9.2.2](#) for guidance on IP records and documentation.

4.4 Method of Assigning Subject Identification

Within each panel, subjects will be randomized to receive either BMS-986165 at one of the doses being evaluated (3mg every other day, 3mg every day, 3 mg twice daily, 6mg twice daily, 12mg every day) or placebo according to a computer-generated randomization scheme prepared by a Randomization Coordinator within the Drug Supply Management Department of BMS Research and Development. Randomization will be stratified by previous treatment with a biologic and region (Japanese vs rest of world).

Enrolled subjects, including those not dosed, will be assigned sequential subject numbers starting with 00001, (e.g., 00001, 00002, 00003.... 00010). Sequential numbering may restart at 00001 for each participating site as the distinct patient identification number (PID) will ultimately be comprised of the site number and subject number, (e.g., 0002 00001). Those enrolled subjects meeting inclusion and exclusion criteria will be eligible to be randomized. Randomization numbers will be assigned prior to dosing.

During the screening visit, the investigative site will call into the enrollment option of the Interactive Web Response System (IWRS) designated by BMS for assignment of a 5-digit subject number that will be unique across all sites. Enrolled subjects, including those not dosed, will be assigned sequential subject numbers starting with 00001, (e.g., 00001, 00002, 00003....

00010). The patient identification number (PID) will ultimately be comprised of the site number and subject number. For example, the first subject screened (i.e., enrolled) at site number 1, will have a PID of 0001 00001. Once it is determined that the subject meets the eligibility criteria following the screening visit, the investigative site will call the IWRS to randomize the subject.

4.5 Selection and Timing of Dose for Each Subject

The BMS-986165 capsules (active or placebo) are provided in blister card kits which contain 48 capsules and will treat the patients for 8 days. The capsules will be arranged in 8 rows each containing four capsules to be taken each morning and two capsules to be taken at night, approximately 12 hours after the morning dose and will contain the appropriate combination of active and placebo to provide the subjects required daily dose (3mg every other day, 3mg every day, 3 mg twice daily, 6 mg twice daily, 12 mg every day, or placebo). It is essential that all patients finish all 8 days of treatment prior to starting a new blister card kit to ensure appropriate doses as identified above. If the subject forgets to take the dose, but remembers within 4 hours of the scheduled dose, then they should take it. If it is past 4 hours, they should miss that dose and take the next scheduled dose. Fasting is not required for drug administration, except on the days scheduled for blood collection under fasting conditions (Days 1, 8, 15, 29, 57 and 85). On these days, the morning dose should be administered at the investigator's site.

4.6 Blinding/Unblinding

Blinding of treatment assignment is critical to the integrity of this clinical study. However, in the event of a medical emergency or pregnancy in an individual subject in which knowledge of the investigational product is critical to the subject's management, the blind for that subject may be broken by the investigator. The subject's safety takes priority over any other considerations in determining if a treatment assignment should be unblinded.

Before breaking the blind of an individual subject's treatment, the investigator should determine that the unblinded information is necessary, (i.e., that it will alter the subject's immediate management). In many cases, particularly when the emergency is clearly not related to the investigational product, the problem may be properly managed by assuming that the subject is receiving active product. It is highly desirable that the decision to unblind treatment assignment be discussed with the medical monitor, but the investigatory always has ultimate authority for the decision to unblind. The principal investigator should only call in for emergency unblinding AFTER the decision to discontinue the subject has been made.

In cases of accidental unblinding, contact the medical monitor and ensure every attempt is made to preserve the blind.

Any request to unblind a subject for non-emergency purposes should be discussed with the medical monitor.

In case of an emergency, the investigator(s) has unrestricted access to randomization information via the IWRS and is capable of breaking the blind through the IWRS system without prior approval from sponsor. Following the unblinding the Investigator shall notify the medical monitor and/or study director.

4.7 Treatment Compliance

At each study visit compliance with study drug will be reinforced. Subject diaries will be used to assist subjects in maintaining an accurate assessment of daily pill intake. Subject diaries and study blister pack will be required to be returned at every visit throughout the study.

4.8 Destruction or Return of Investigational Product

For this study, IP (those supplied by BMS, a vendor or sourced by the investigator) such as partially used study drug containers, vials and syringes may be destroyed on site.

If...	Then...
IP supplied by BMS (including its vendors)	Any unused IP supplied by BMS can only be destroyed after being inspected and reconciled by the responsible Study Monitor unless IP containers must be immediately destroyed as required for safety, or to meet local regulations (e.g., cytotoxics or biologics). If IP will be returned, the return will be arranged by the responsible Study Monitor.
IP sourced by site, not supplied by BMS (or its vendors) (examples include IP sourced from the sites stock or commercial supply, or a specialty pharmacy)	It is the investigator's or designate's responsibility to dispose of all containers according to the institutional guidelines and procedures.

It is the investigator's or designate's responsibility to arrange for disposal, provided that procedures for proper disposal have been established according to applicable federal, state, local, and institutional guidelines and procedures, and provided that appropriate records of disposal are kept. The following minimal standards must be met:

- On-site disposal practices must not expose humans to risks from the drug.
- On-site disposal practices and procedures are in agreement with applicable laws and regulations, including any special requirements for controlled or hazardous substances.
- Written procedures for on-site disposal are available and followed. The procedures must be filed with the site's SOPs and a copy provided to BMS upon request.
- Records are maintained that allow for traceability of each container, including the date disposed of, quantity disposed, and identification of the person disposing the containers. The method of disposal, (i.e., incinerator, licensed sanitary landfill, or licensed waste disposal vendor) must be documented.
- Accountability and disposal records are complete, up-to-date, and available for the monitor to review throughout the clinical trial period.

It is the investigator's or designate's responsibility to arrange for disposal of all empty containers.

If conditions for destruction cannot be met the responsible BMS study monitor will make arrangements for return of IP provided by BMS (or its vendors). Destruction of non-IP sourced by the site, not supplied by BMS, is solely the responsibility of the investigator or designate.

Please refer to [Section 9.2.2](#) for additional guidance on IP records and documentation

4.9 Retained Samples for Bioavailability / Bioequivalence

Not Applicable.

5 STUDY ASSESSMENTS AND PROCEDURES

5.1 Flow Chart/Time and Events Schedule

Study assessments and procedures are presented in [Table 5.1-1](#) and [Table 5.1-2](#).

Table 5.1-1: Screening Procedural Outline (IM011011)

Procedure	Screening Visit	Notes
Eligibility Assessments		
Informed Consent	X	A subject is considered enrolled only when a protocol specific informed consent is signed.
Inclusion/Exclusion Criteria	X	
Medical History	X	Include any toxicities or allergy related to previous treatments.
Safety Assessments		
Physical Examination (PE)	X	
Physical Measurements	X	Includes height, weight, and BMI.
Vital Signs	X	Includes (ear or oral) body temperature, respiratory rate, seated blood pressure and heart rate. Blood pressure and heart rate should be measured after the subject has been resting quietly for at least 5 minutes.
Electrocardiogram (ECGs)	X	ECGs should be recorded after the subject has been supine for at least 5 minutes. See Section 5.3.5
Chest X-ray	X	Chest x-ray is required if not performed within 6 months of Screening visit, documentation must be on file. See Section 5.3.4
Laboratory Tests		
Urinalysis	X	Subjects are required to fast for at least 10 hours prior to the collection of specimens for clinical laboratory tests. See Section 5.3.2
Hematology	X	Complete Blood Count (CBC) with differential Subjects are required to fast for at least 10 hours prior to the collection of specimens for clinical laboratory tests. See Section 5.3.2
Chemistry Panel	X	Subjects are required to fast for at least 10 hours prior to the collection of specimens for clinical laboratory tests. See Section 5.3.2
Serology	X	Includes Hepatitis C antibody, Hepatitis B surface antigen, Hepatitis B core antibody, and HIV-1 and HIV-2 antibodies. See Section 5.3.2
Tuberculosis Test	X	In accordance with BMS standard testing. See Section 5.3.4 of the protocol for more details.
Pregnancy Test (urine)	X	For WOCBP only.

Table 5.1-1: Screening Procedural Outline (IM011011)

Procedure	Screening Visit	Notes
Follicle Stimulating Hormone (FSH)	X	Women only, Refer to Section 3.3.3 .
Study Procedures		
PASI Score Assessment	X	See Section 5.4
BSA Assessment	X	See Section 5.4
Adverse Event Reporting		
Monitor for Serious Adverse Events	X	All SAEs must be collected from the date of subject's written consent until 28 days post discontinuation of dosing or subject's participation in the study if the last scheduled visit occurs at a later time.

Table 5.1-2: On Treatment Procedural Outline for IM011011

Procedure	D1	D8 ±3 day	D15 ±3 day	D29 ±3 day	D57 ±3 day	D85 ±7 days ^a	Follow-Up visit D115	Notes
Safety Assessments								
Full Physical Examination (PE)	X			X	X	X	X	See Section 5.3.3
Targeted Physical Examination		X	X					See Section 5.3.3
Physical Measurements	X			X	X		X	Weight only
Vital Signs	X	X	X	X	X	X	X	Includes (ear or oral) body temperature, respiratory rate, seated blood pressure and heart rate. Blood pressure and heart rate should be measured after the subject has been resting quietly for at least 5 minutes.
Electrocardiograms (ECGs)	X	X	X	X	X	X	X	See Section 5.3.5
Laboratory Tests								
Hematology	X*	X	X	X	X	X	X	Including CBC with differential See Section 5.3.2 *predose (Subjects are required to fast for at least 10 hours prior to the collection of specimens for clinical laboratory tests Day 1)
Chemistry Panel	X*	X	X	X	X	X	X	See Section 5.3.2 *predose (Subjects are required to fast for at least 10 hours prior to the collection of specimens for clinical laboratory tests Day 1)
High sensitivity CRP	X*			X	X	X		See Section 5.3.2

Table 5.1-2: On Treatment Procedural Outline for IM011011

Procedure	D1	D8 ±3 day	D15 ±3 day	D29 ±3 day	D57 ±3 day	D85 ±7 days ^a	Follow-Up visit D115	Notes
(hsCRP)								*predose
Fasting Lipid Panel	X*					X		Subjects are required to fast for at least 10 hours prior to the collection of specimens for clinical laboratory tests See Section 5.3.2 *predose
Fasting Plasma Glucose	X*					X		Subjects are required to fast for at least 10 hours prior to the collection of specimens for clinical laboratory tests See Section 5.3.2 *predose
Fasting C-peptide	X*					X		Subjects are required to fast for at least 10 hours prior to the collection of specimens for clinical laboratory tests See Section 5.3.2 *predose
Urinalysis	X*	X	X	X	X	X	X	See Section 5.3.2 *predose (Subjects are required to fast for at least 10 hours prior to the collection of specimens for clinical laboratory tests on Day 1)
Serum Immunoglobulin Levels (IgM, IgG, IgA, IgE)	X*			X	X	X		See Section 5.3.2. *predose
Pregnancy Test (Urine)	X*			X	X	X	X	Female subjects only. *All women must have a negative pregnancy prior to dosing on Day 1.
Adverse Event Reporting								

Table 5.1-2: On Treatment Procedural Outline for IM011011

Procedure	D1	D8 ±3 day	D15 ±3 day	D29 ±3 day	D57 ±3 day	D85 ±7 days ^a	Follow-Up visit D115	Notes
Monitor for non-Serious Adverse Events	X	X	X	X	X	X	X	See Section 6.2 .
Monitor for Serious Adverse Events	X	X	X	X	X	X	X	See Section 6.1
Pharmacokinetic (PK) Assessments								
Blood PK Sampling	X*	X	X	X	X	X		*Pre and post-dose. See Section 5.5 and
Study Procedure								
PASI Score Assessment	X	X	X	X	X	X	X	See Section 5.4
BSA Assessment	X	X	X	X	X	X	X	See Section 5.4
sPGA	X	X	X	X	X	X	X	See Section 5.4
Subject Global Assessment of Pain VAS	X	X	X	X	X	X	X	See Section 5.4
Medical Photography (skin)	X			X		X		At selected sites only. See Section 5.3.6
Skin Biopsy	X		X			X		See Section 5.3.7
Biomarker Assessments								
Target Engagement	X	X	X					See Section 5.6 (TE samples will be collected in the 1st 100 dosed subjects)
Blood PD Sampling	X	X	X	X	X	X	X	See Section 5.6
TBNK	X			X		X		See Section 5.6
Blood PaxGene RNA	X			X	X	X	X	See Section 5.6
CV/Metabolic blood sample (Serum)	X			X		X		See Section 5.6

Table 5.1-2: On Treatment Procedural Outline for IM011011

Procedure	D1	D8 ±3 day	D15 ±3 day	D29 ±3 day	D57 ±3 day	D85 ±7 days ^a	Follow-Up visit D115	Notes
CV/Metabolic blood sample (Plasma)	X			X		X		See Section 5.6
Other Assessments								
DLQI	X			X	X	X	X	See Section 5.4
Clinical Drug Supplies								
Dispense Study Drug	X	X	X	X	X			Subjects will be supplied with enough oral study drug (or placebo) to cover the intervals between study visits. See Section 4

^a Evaluations performed prior to study discharge, or for subjects who are prematurely discontinued. In addition for subjects who are prematurely discontinued, the following should also be performed prior to study discharge: D85 procedure

Abbreviations: D = Day

5.1.1 Retesting During Screening or Lead-in Period

Retesting of laboratory parameters and/or other assessments within any single Screening or Lead-in period will be permitted (in addition to any parameters that require a confirmatory value).

Any new result will override the previous result (i.e., the most current result prior to Randomization) and is the value by which study inclusion will be assessed, as it represents the subject's most current, clinical state.

Laboratory parameters and/or assessments that are included in [Table 5.1-1](#), Screening Procedural Outline may be repeated in an effort to find all possible well-qualified subjects. Consultation with the medical monitor may be needed to identify whether repeat testing of any particular parameter is clinically relevant.

5.2 Study Materials

The site will provide all required materials for the tests performed locally (i.e., relevant clinical laboratory tests and urine drug screens). The site will have available a well-calibrated scale for recording body weight, a 12-lead ECG machine, and a calibrated sphygmomanometer and thermometer for vital signs assessments. A current and fully-stocked basic cardiac life support (BCLS) cart will be immediately available on the premises. The site will have urine collection containers, a refrigerated centrifuge, a monitored and alarmed refrigerator, and freezer (-20°C or below), as well as containers and dry ice for shipment and storage of blood and urine samples. The site will provide all materials required for accurate source documentation of study activities and for housing the subjects during the study.

Subjects will be provided with cooler bags and gel packs for transporting BMS-986165/matched placebo as it needs to be kept refrigerated,

BMS will provide a BMS-approved protocol and any amendments or administrative letters (if required), and investigator brochure. Case report forms (electronic or hard copy) will be provided by BMS. The Central Laboratory will provide labels and tubes for the collection of blood samples for PK and biomarker samples.

Study supplies and documents (eg, electronic Case Reports Forms, patient drug logs, etc.) will be provided to the study center by BMS. Subject dosing diaries will be provided for each subject for completion throughout the study. IVRS/IWRS worksheets and instruction manuals will be provided by the IVRS/IWRS vendor.

5.3 Safety Assessments

On Day 1, the results of all assessments must be reviewed to assure that eligibility requirements are met before contacting the Central Randomization System for the subject's randomization assignment.

Subjects who terminate early will complete the Day 85/Early Termination (ET) Visit assessments. The Early Termination Visit should be as soon as possible after the last dose of

study medication (investigational product) and prior to the subject receiving a prohibited concomitant medication.

All assessments should be performed or administered prior to study drug administration unless otherwise indicated.

Every effort must be made to ensure the same evaluator will complete the assessments for each subject at all visits.

Only data for the procedures and assessments specified in this protocol should be submitted to BMS on a case report form. Additional procedures and assessments may be performed as part of your institutional or medical practice standard of care; however, data for these assessments should remain in the subject's medical record and should not be provided to BMS, unless specifically requested from the sponsor.

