3.3.1 Inclusion Criteria

1. Signed Written Informed Consent

- a) Subjects is willing to participate in the study and has signed the informed consent

2. Target Population

- a) Male and female subjects with a diagnosis of plaque psoriasis for ≥ 6 months
- b) Body mass index (BMI) 18-40 kg/m² and total body weight > 50 kg (110 lb)
- c) Deemed by Investigator to be eligible for phototherapy or systemic therapy
- d) Psoriatic plaques must cover $\geq 10\%$ of body surface area (BSA)
- e) Psoriasis Area and Severity Index (PASI) score ≥ 12 and sPGA ≥ 3

3. Age and Reproductive Status

- a) Males and Females, ages 18 or age of majority to 70 years, inclusive
- b) Women of childbearing potential (WOCBP) must have a negative serum or urine pregnancy test (minimum sensitivity 25 IU/L or equivalent units of HCG) within 24 hours prior to the start of study drug.
- c) Women must not be pregnant, lactating, breastfeeding or planning pregnancy during the study period
- d) Women of childbearing potential (WOCBP) must agree to follow instructions for method(s) of contraception for the duration of treatment with study drug(s) BMS-986165 plus 5 half-lives of study drug plus 30 days (duration of ovulatory cycle) for a total of 33 days post-treatment completion
- e) Males who are sexually active with WOCBP must agree to follow instructions for method(s) of contraception for the duration of treatment with study drug(s) BMS-986165 plus 5 half-lives of the study drug plus 90 days (duration of sperm turnover) for a total of 93 days post-treatment completion. In addition, male subjects must be willing to refrain from sperm donation during this time.
- f) Azoospermic males are exempt from contraceptive requirements. WOCBP who are continuously not heterosexually active are also exempt from contraceptive requirements, and still undergo pregnancy testing as described in this section.

Investigators shall counsel WOCBP and male subjects who are sexually active with WOCBP on the importance of pregnancy prevention and the implications of an unexpected pregnancy. Investigators shall advise on the use of highly effective methods of contraception ([Appendix 1](#)) which have a failure rate of < 1% when used consistently and correctly.

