5.3.5 ECG

12-lead ECGs should be collected at times specified in [Table 5.1-1](#) and [Table 5.1-2](#). All scheduled ECGs should be performed after the subject has rested quietly for at least 5 minutes in a supine position. When the timing of the measurements coincides with a blood collection, the

ECG should be obtained prior to the nominal time of the blood collection, blood pressure, and pulse rate.

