5.5.1 Pharmacokinetics: Collection and Processing

Table 5.5.1-1 lists the sampling schedule to be followed for the assessment of pharmacokinetics. Further details of blood collection and processing will be provided to the site in the procedure manual.

Table 5.5.1-1: Pharmacokinetics Sampling Schedule

Study Day of Sample Collection	Event	Time (Relative To BMS-986165 Dose) Hour: Min	BMS-986165 Blood Sample for PK	Notes
1	predose ^a	00:00	X	
1		00:30	X	
1		01:00	X	
8	Predose ^a	00:00	X	
15	Predose ^a	00:00	X	
15*		00:30	X	*These post-dose samples maybe drawn at any scheduled visit day after Day 15 (i.e On Day 29, 57 or 85)
15*		01:00	X	
15*		04:00	X	
15*		06:00	X	
29	Predose ^a	00:00	X	
57	predose ^a	00:00	X	
85	predose ^a	00:00	X	

^a predose samples must be drawn before the morning dose on the Visit Day

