7.6.7 Electrocardiogram

Summary statistics (n, mean, standard deviation, median, minimum, and maximum) will be presented for each ECG parameters and the corresponding changes from baseline by treatment and visit. The baseline value is defined as the last measurement before the first dose. ECG readings will be evaluated by the Investigator and abnormalities, if present, will be listed.

The frequency distribution of subjects' maximum recorded post-dose QTcF, PR, QRS and Δ QTcF will be summarized by treatment group for the following ranges:

- QTcF: $QTcF \leq 450$ msec, $450 \text{ msec} < QTcF \leq 480$ msec, $480 \text{ msec} < QTcF \leq 500$ msec, $QTcF > 500$ msec
- PR: $PR \leq 200$ msec, $PR > 200$ msec
- QRS: $QRS \leq 120$ msec, $QRS > 120$ msec
- Δ QTcF: $\Delta QTcF \leq 30$ msec, $30 \text{ msec} < \Delta QTcF \leq 60$ msec, $\Delta QTcF > 60$ msec

Individual QTcF, PR, QRS or Δ QTcF values meeting the above criteria will be flagged in the data listing.

The following summary tables will be provided:

- Electrocardiogram Summary: Summary Statistics for ECG Values and changes from baseline
- Frequency Distribution of Maximum Post-Dose ECG Interval

The following by-subject listings will be provided:

- Electrocardiogram (ECG) Results: visit, date, study day, heart rate (bpm), interval (PR, QRS, QT, QTC), interpretation of findings.
- Investigator Identified Abnormal ECG Results: visit, date, study day, heart rate (bpm), interval (PR, QRS, QT, QTC), interpretation of findings
- Subjects with Heart Rates and Out-Of-Range ECG Intervals: visit, date, study day, time, heart rate (bpm), interval (PR, QRS, QT, QTcB, QTcF), change from baseline (HR, PR, QRS, QT, QTcB, QTcF).

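### Scheduled on-treatment ECGs default to before the morning dose, so the SAP's ECG outlier table would describe essentially trough readings and, under linear PK, compare the two 12 mg/day arms in the opposite order to their peaks

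*Protocol*

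**What the plan says.** Protocol Section 5.3, the parent of the ECG subsection, sets a general rule: "All assessments should be performed or administered prior to study drug administration unless otherwise indicated". Table 5.1-2 schedules one ECG at each of Days 1, 8, 15, 29, 57, 85 and 115, with no clock time and no pre/post-dose mark, and refers to Section 5.3.5. That section adds only that, when a blood draw coincides, the "ECG should be obtained prior to the nominal time of the blood collection, blood pressure, and pulse rate".

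Section 4.5 covers dosing on Days 1, 8, 15, 29, 57 and 85: "On these days, the morning dose should be administered at the investigator's site". The footnote to Table 5.5.1-1 says that "predose samples must be drawn before the morning dose on the Visit Day". Post-dose times are marked for PK only: 0.5 and 1 h on Day 1, and 0.5, 1, 4 and 6 h on Day 15. Of the Day 15 series the table notes: "These post-dose samples maybe drawn at any scheduled visit day after Day 15".

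SAP 7.6.7 takes as baseline the last ECG before first dosing. It then plans a table titled "Frequency Distribution of Maximum Post-Dose ECG Interval", covering QTcF, PR, QRS and change in QTcF by arm. One listing carries a time field, but no summary or listing uses time since last dose.

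**The concern.** Safety and tolerability is a primary objective (Protocol 1.3.1), and ECGs are a named component of how it is assessed (Protocol 8.3.1, SAP 4.3). If the scheduled on-treatment ECGs all precede the dose, a concentration-related effect on QTcF, PR or QRS is looked for when concentration is at or near its lowest. A reader of the table's upper categories (QTcF above 480 or 500 msec, change above 60 msec) would not know this.

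The comparison between arms is also affected. The 6 mg BID and 12 mg QD arms give the same daily dose, but a predose reading falls about 12 h after the last dose in one and about 24 h in the other. A side-by-side ECG table could then suggest that once-daily dosing is the milder of the two at the very arm with the higher peak.

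**Working it through.** **Plan's own figure.** The documents give no figure for ECG timing. Their only safety calculation is the chance of seeing at least one adverse event in 42 subjects, 1 − (1 − p)^42. This gives 34.4%, 88.4% and 98.8% at p = 1%, 5% and 10%, matching the stated 34%, 88% and 99%. The present point does not change it.

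**Step 1: timing from the text.**
- The default is predose (5.3). The ECG row and 5.3.5 contain no exception. Where post-dose timing is wanted, as for PK, the protocol marks it.
- On Days 8, 29, 57 and 85 the only fixed PK draw is predose, so placing the ECG before the draw also places it before the dose.
- Day 1 supplies the baseline. Day 115 is 30 days after Day 85 and off drug.
- The blister layout is four capsules in the morning and two at night (4.5). 12 mg QD needs four 3 mg capsules and so fits only the morning slot.
- A predose ECG is therefore about 24 h post-dose for 12 mg QD and about 12 h for 6 mg BID.

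**Step 2: direction.** Assume linear PK at steady state and let Cq(t) be the 12 mg QD curve. The 6 mg BID curve is ½[Cq(t) + Cq(t+12)].
- Predose: ½[Cq(24) + Cq(12)] exceeds Cq(24) whenever Cq(12) > Cq(24).
- Peak: an average of two points on the QD curve cannot exceed the QD peak.
- Daily AUC is the same in both arms.

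The direction needs no half-life value.

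**Step 3: size, by assumption.** The readable text gives neither half-life nor Tmax. The contraception rule adds 5 half-lives to 30 days "for a total of 33 days post-treatment completion", so 5 half-lives = 3 days and the half-life is 72/5 = 14.4 h. If the 3 days were rounded up from just over 2, it could be as short as 48/5 = 9.6 h. I take 8 to 14.4 h; the 8 h floor is an assumption. The model is one-compartment with first-order absorption rate ka, from instantaneous down to 0.3/h.

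For instantaneous absorption, peak = D/(1 − 2^(−τ/t½)) and predose = peak × 2^(−τ/t½). At 14.4 h:
- 12 mg QD: 2^(−24/14.4) = 0.315; peak 12/0.685 = 17.5; predose 5.5.
- 6 mg BID: 2^(−12/14.4) = 0.561; peak 6/0.439 = 13.7; predose 7.7.

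| t½, ka | 12 mg QD peak / predose (share) | 6 mg BID peak / predose (share) | Predose BID/QD | Peak BID/QD |
|---|---|---|---|---|
| 8 h, instantaneous | 13.71 / 1.71 (12.5%) | 9.28 / 3.28 (35%) | 1.91 | 0.68 |
| 14.4 h, instantaneous | 17.52 / 5.52 (31%) | 13.67 / 7.67 (56%) | 1.39 | 0.78 |
| 14.4 h, 1/h | 15.32 / 5.80 (38%) | 12.23 / 8.06 (66%) | 1.39 | 0.80 |
| 14.4 h, 0.3/h | 13.27 / 6.56 (49%) | 11.22 / 8.94 (80%) | 1.36 | 0.85 |

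(Relative units, volume set to 1.) Across half-lives of 3 to 24 h and Tmax of 0 to 4 h, the predose ratio stays above 1 (1.21 to 8.5) and the peak ratio below 1 (0.53 to 0.87).

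**The case against.** Several stronger readings are tempting, and the documents do not support them.

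- **That no ECG can ever fall near peak.** The early-termination ECG follows the last dose at an uncontrolled time (5.3). Unscheduled safety visits are allowed (3.1), and significant ECG worsening is reportable as an adverse event (6.7). On the serial-PK day, 5.3.5 could be read as permitting an ECG before a later draw. A post-dose ECG is unscheduled, not forbidden. None of these routes gives systematic post-dose readings by arm, however, and the permissive reading of 5.3.5 would leave timing to the site.
- **That total exposure order is reversed.** It is not. Only the peak and trough orders differ.
- **That the SAP table is mislabelled.** Since baseline is defined as before the first dose, post-dose may simply mean after first dosing. That is a fair reading. The label is ambiguous rather than wrong.
- **That a cardiac effect is being missed.** The readable text names no cardiac concern. Background sections are redacted and the Investigator Brochure is not available, so whether ECGs near peak were already characterised cannot be judged.

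Three further points stand. The ECG summary is descriptive, with no test between 6 mg BID and 12 mg QD. Predose PK samples pair with predose ECGs, which allows some concentration-based reading. The percentages depend on assumed kinetics, and a delay between concentration and effect would soften the argument.

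**Conclusion.** The point holds as a cheap improvement to the safety assessment. By the protocol's default, the scheduled on-treatment ECGs are predose, and the SAP's outlier table would consist essentially of trough readings without saying so. This rests on the text alone.

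That 12 mg QD has the higher peak and the lower predose concentration rests on linear PK and on the QD level at 12 h exceeding that at 24 h. Its size is illustrative. With half-lives of 8 to 14.4 h and absorption from instantaneous to 0.3/h, predose is about 13-49% of peak for 12 mg QD and 35-80% for 6 mg BID. No error rate, sample size or efficacy conclusion is affected.

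**What to change.** **Protocol Table 5.1-2 and Section 5.3.5.** At the visit where the serial post-dose PK samples are drawn (Day 15, or the later visit used), take that visit's already scheduled ECG after the dose. Place it immediately before one named post-dose PK sample, which the sponsor selects as closest to the known Tmax. Give the ECG its own tight window. The PK windows in Section 5.5.2 are ±1 h for samples in the first two hours and ±3 h for the 4 and 6 h samples, so an ECG tied to the 0.5 h sample under those windows could be effectively predose. Keep the other ECGs predose, and record the actual time since last dose for every ECG.

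**SAP 7.6.7.** Tabulate predose and post-dose readings separately by arm against placebo. State whether post-dose in the outlier table means after the first dose or after the visit-day dose.

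**Cost.** Protocol wording, one time field and one split table, with no extra ECG, visit or staff. One visit loses its predose ECG, and the post-dose reading is not time-matched to the predose Day 1 baseline. Comparison with placebo at the same time point mitigates this.
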